### **7.4 DAYS 1 THROUGH 84 – BREATH SAMPLING**

Study participants will be instructed to use the breath sensor daily for the duration of the study, with a recommendation that they do at least 4 breath samples a day, spread over the course of the day. This suggested use pattern is provided in the labeling materials and during the screening phone call but breath sensor use is ultimately at the discretion of the participant. Participants may receive twice weekly text instructions to sync their breath sensor data to the app. This will enable the study team to track participant breath sensor data as the study proceeds.

### **7.5 DAYS 1 THROUGH 84 – STUDY QUESTIONNAIRES**

Participants will receive periodic electronic questionnaires via email (Survey Monkey) that focus on attitudes towards quitting, smoking behavior, and participant feedback on breath sensor set-up, user experience, impact and commercialization (Section 7.7).

Participants will receive periodic reminders from study staff to complete the questionnaires via email, text or phone, as needed. All participants will receive the 28-day and 84-day questionnaires, regardless of previous completion of questionnaires.

### **7.6 DAY 84 AND STUDY COMPLETION**

Upon completion of the study, the participant will receive the electronic final questionnaire; the participant will have up to 14 days to complete the final questionnaire once it has been emailed to them. The participant will be asked to send the Pivot Breath Sensor back using a provided pre-paid mailer.

**7.7 SCHEDULE OF STUDY ACTIVITIES**

Event	Screening 	Registration	1	7	14	21	28	56	84	84-98
Eligibility confirmed	X									
Phone call	X		X 							
Informed consent		X								
Receive breath sensor 			X							
Active use of breath sensor			X	X	X	X	X	X	X	
Survey		X		X	X	X	X	X	X	
- Baseline and demographic data		X								
- Access device settings				X	X	X	X	X	X	
- Feedback: breath sensor set-up				X						
- CPD		X		X	X	X	X	X	X	
- Desire to quit		X		X	X		X	X	X	
- Difficulty to stay quit		X		X	X		X	X	X	
- Stage of Change		X		X	X		X	X	X	
- Readiness to quit		X		X	X		X	X	X	
- Confidence to quit		X		X	X		X	X	X	
- Goals		X		X	X		X	X	X	
- Point prevalence abstinence					X	X	X	X	X	
- Quit attempts		X			X		X	X	X	
- CO reading understanding				X	X		X	X	X	
- Feedback: breath sensor experience and use				X	X		X	X	X	
- Feedback: impact of breath sensor				X	X	X	X			
- Feedback: commercialization					X		X			
Final questionnaire										X
Return breath sensor										X
Study completion										X

1 Screening is a phone call to prescreened candidates based on their responses to an online screening questionnaire.

2 Pivot Breath Sensor received by participant only after confirmation of eligibility and provision of electronic informed consent.

3 Optional phone call to assist with breath sensor set-up as needed

## 8. DATA COLLECTION

Study personnel will collect information from the participant over the course of the study including:

- Age
- Gender
- Pregnancy status (self-reported) in women
- Race/ethnicity
- Type of smartphone participant used (iPhone or Android)
- Number of years smoking
- Quit attempts
  - Past 12 months
  - During the study
- Number of cigarettes currently smoked per day (CPD)
- 7-day point prevalence abstinence (PPA)
- 30-day point prevalence abstinence (PPA)
- Use of any combustible, inhaled tobacco product other than cigarettes (pipes, cigars, cigarillos, etc.), any electronic cigarette product (e-cigs, vape, vapor), and any other inhaled combustible material
- Use of smoking cessation medications
- Participation in a smoking cessation program
  - Past
  - Present
- Ability to access settings (sensor battery life reading and “Sync Now” function) in the Sensor-Only app
- Attitudes towards smoking
  - Desire to quit (y/n)
  - Stage of Change
  - Readiness to quit (scale 1-10)
  - Confidence to quit (scale 1-10)
  - Perceived difficulty of staying quit (scale 1-10)
  - Goals
- Feedback on breath sensor set-up
  - Ease/difficulty getting started with the breath sensor (scale 1-5)
  - Ease/difficulty following directions on the breath sensor screen (scale 1-5)
  - Ease/difficulty of to understand error messages on breath sensor screen if applicable (scale 1-5)
- Feedback on breath sensor experience and use
  - How would you improve the Pivot Breath Sensor experience?
  - Please describe any issues you’ve had with the breath sensor
  - How likely are you to recommend the Pivot Breath Sensor to a friend/colleague? (scale 1-10)
  - Do you use the breath sensor at least once a day (if not, why?)
  - Are you using the breath sensor as often as you did in the beginning of the program? (if not, why?)

- Which of the following best describes your thoughts on the Pivot Breath Sensor? ('nothing else can help me with smoking' to 'it will not help me with smoking')
- Feedback on impact of breath sensor
  - Comprehension of CO and CO values as they relate to smoking behavior
  - How has seeing your CO values impacted you as it relates to:
    - your feelings?
    - learning?
    - your thoughts about smoking and daily smoking behavior?
    - your thoughts about quitting?
  - How has the breath sensor affected your motivation to quit smoking? (increase, no change, decrease)
  - How has the breath sensor affected the number of cigarettes you smoke per day? (increase, no change, decrease)
  - Which of the following best describes the Pivot Breath Sensor's ability to help someone quit smoking? ('extremely helpful' to 'makes quitting smoking harder')
  - Which of the following best describes what you have learned from using the Pivot Breath Sensor ('really unique/key insights' to 'I am more confused after using the sensor')
  - Has the breath sensor taught you about your CO levels? (y/n)
  - Has the breath sensor taught you about your smoking behavior? (y/n)
  - What are your initial impressions of the booklet titled "The Pivot CO Sensor: Prepare to be blown away", found inside the sensor box?
  - Do you have a better understanding about CO levels and your smoking behavior because of the breath sensor? (y/n)
  - How well do you understand CO in general? (1 = not at all, 10 = completely understand)
  - How well do you understand your CO levels and trends as they relate to your smoking behavior? (1 = not at all, 10 = completely understand)
- Feedback on commercialization
  - Hypothetical: if it was commercially available, would you be interested in buying the Pivot Breath Sensor? Why or why not?
  - What is a reasonable price for the Pivot Breath Sensor? Why?
  - How would you describe your need for the Pivot Breath Sensor? ('I really need this product' to 'I am not interested at all in this product')

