Data Collection	Data will be collected through an application (app) that the study participants install on their smartphone (the Sensor-Only app) and through participant completion of emailed online questionnaires.
Performance Variable	Assessment of the role of the Pivot Breath Sensor in attitudes towards quitting smoking and in smoking behavior: 

• Attitudes towards quitting: Stage of Change, desire to quit, confidence to quit, and difficulty to quit.

• Smoking behavior: quit attempts, change in cigarettes per day (CPD), smoking cessation via 7-and 30-day point prevalence abstinence.

• Participant feedback on the set-up, use experience, impact and commercialization of Pivot Breath Sensor.

Performance Endpoint and Analysis	Change from baseline measurement

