### Pivot Breath Sensor.

The primary endpoint will assess any change in the proportion of participants' Stage of Change response at day 28 compared to baseline

- A positive outcome is defined as a participant responding as more ready to quit. For example, a change in response from seriously thinking of quitting smoking "...within the next 6 months" at baseline to seriously thinking of quitting smoking "...within the next 30 days" at day 28.

The secondary endpoints include:

- The proportion of participants who reported  $\geq 1$  quit attempt by day 28; will be compared to zero
  - A quit attempt is defined as answering  $\geq 1$  to the following question: "Since you began using the Pivot Breath Sensor, how many times have you tried to quit smoking where you've gone at least 1 day without smoking a cigarette, even a single puff?"
- The proportion of participants who reduced their cigarettes per day (CPD) by  $\geq 50\%$  by day 28, compared to baseline

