## 10.2 ANALYSIS

Changes in measurements from baseline will be assessed at different timepoints in the study. Participants will serve as their own controls and comparisons will be made to no change. One sample t-test will be used for numerical data. Fisher's Exact or Chi square tests will be used for categorical data. Analyses will be conducted to calculate mean (SD) for normally distributed variables for actual data or mean (SE) for modeled data and median (interquartile range) values in instances of non-normally distributed variables.

McNemar test will be used for 2-category match-paired data. Cohen kappa statistic will be used for 3-category match-paired data. To evaluate changes in attitudes or cigarettes smoked per day over time, repeated measures linear mixed model analyses will be performed using a compound symmetric correlation matrix to model the repeated measures within subjects. To make specific comparisons across time, F statistics will be computed using the results from the model. Statistical significance is set at  $P < .05$ .

Analyses for the outcomes will be evaluated for only those who complete the survey (i.e. completer) and assessed to take into account missing data. To be included in any completer analysis the participant must provide a baseline response and the outcome response. For outcomes that are missing data, these will be assessed pending the data type.

For categorical data, the last response post-baseline will be carried forward for the day 28 analysis and the last response post-28 days will be carried forward for the day 84 assessment. If there is not any data to carry forward, the data will be considered unchanged from baseline. Numerical data will use linear mixed modeling.

All deviations from the study protocol will be identified, recorded and analyzed.

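### The quit-attempt endpoint has no like-for-like baseline, so the general own-control and missing-data rules in Section 10.2 do not fit it

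*Combined protocol and SAP*

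**What the plan says.** Section 8 lists two windows for quit attempts, "Past 12 months" and "During the study". The "Quit attempts" row of the schedule in Section 7.7 is marked at Registration and at days 14, 28, 56 and 84.

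The secondary endpoint in Section 6.3 is the proportion reporting at least one attempt by day 28. Its item begins "Since you began using the Pivot Breath Sensor, how many times have you tried to quit smoking" and requires at least one smoke-free day. The comparator is given there as "quit attempt by day 28; will be compared to zero". Section 6.6 sizes the same endpoint differently: 25% expected, against an external rate of about 5% a month that rests on a 65.4% past-year prevalence in the general population.

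The general rules make no exception for this endpoint. The Synopsis describes the endpoint analysis as "Change from baseline measurement". Section 10.2 says "Participants will serve as their own controls". For categorical outcomes it carries the last post-baseline response forward to day 28 and then adds: "If there is not any data to carry forward, the data will be considered unchanged from baseline".

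**The concern.** A within-person comparison needs the same question over the same length of time before and after. Here the pre-study window appears to be 12 months and the endpoint window about 28 days, so the baseline answer cannot act as a control for the day-28 answer.

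Two things are at stake. First, the study has no reference for this endpoint from its own participants. A test against zero is uninformative, and the 5% rate describes a general population, whereas the enrolment quotas require at least 20% planning to quit within 30 days and hold those not interested below 20%. Second, the missing-data rule has two possible readings for this endpoint, and they give materially different results. If the recorded baseline answer is carried, pre-study attempts are counted as on-study attempts.

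**Working it through.** **1. The windows.** The item marked at Registration cannot refer to the study period, which leaves the 12-month window as the only pre-study one listed. This is an inference, since the Baseline Questionnaire itself is redacted. The ratio of windows is 365/28, about 13.

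**2. The plan's own figure.** For a one-sample proportion, two-sided 0.05 and 80% power:

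n = [(1.960·√(p0(1−p0)) + 0.842·√(p1(1−p1))) / (p1−p0)]²

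With p0 = 0.05 and p1 = 0.25 this gives 15.67, rounded up to 16, as Section 6.6 states. The same formula for 10% against 5% gives 184.8, rounded up to 185, again as stated. The n of 16 uses no within-person baseline, so the difference in windows does not alter it.

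**3. The comparators.**
- Zero: if the true proportion were zero, one attempt by one participant would reject it.
- 5%: simple division of 65.4% gives 65.4/12 = 5.45% a month, or 65.4 × 28/365 = 5.0% per 28 days. A constant-hazard conversion gives 1 − 0.346^(28/365) = 7.8% per 28 days, or 1 − 0.346^(1/12) = 8.5% a month. The benchmark therefore depends on the conversion chosen.

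**4. The missing-data rule.** The documents give no attrition rate, so the inputs are assumptions:
- The fraction m with neither a day-14 nor a day-28 response is 5%, 10% or 15.9%. The last is (220 − 185)/220, that is, all the enrolment headroom lost.
- 65.4% of these participants had a past-year attempt, borrowed from the general-population figure in Section 6.6.

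With true day-28 rate p, carrying the 12-month answer reports (1−m)·p + m·0.654. Coding no attempt reports (1−m)·p.

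| m | p = 5%: 12-month answer carried | p = 5%: no attempt | p = 25%: 12-month answer carried | p = 25%: no attempt |
|---|---|---|---|---|
| 5% | 8.0% | 4.75% | 27.0% | 23.8% |
| 10% | 11.0% | 4.5% | 29.0% | 22.5% |
| 15.9% | 14.6% | 4.2% | 31.4% | 21.0% |

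With all 220 analysed, an exact upper-tail test of 5% at level 0.025 rejects at 19 or more attempters. If the true rate is 5% and the 12-month answer is carried, it rejects with probability of about 40%, 90% and 99.7% for the three values of m.

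**5. Cost of a matched baseline item.** For McNemar with independent responses, p10 = p_after(1−p_before), p01 = p_before(1−p_after), pd = p10 + p01 and d = p10 − p01:

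n = [1.960·√pd + 0.842·√(pd − d²)]² / d²

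With p_after = 25%:
- p_before = 5%: pd = 0.275, d = 0.20, n = 51.5, so 52.
- p_before = 8%: pd = 0.29, d = 0.17, n = 76.4, so 77.
- p_before = 12%: pd = 0.31, d = 0.13, n = 141.6, so 142.

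All are below the 185 already planned for. The 8% case is near the constant-hazard figure in step 3; the 12% case is an assumption.

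**The case against.** The strongest reply is that the plan never specifies a within-person test here. The endpoint-specific text compares with zero and the sample size uses an external 5%; the own-control and change-from-baseline statements are general. A reader might infer that the planned analysis sets 65.4% before against 25% after and would show a fall. The documents do not support that: no section prescribes that comparison for this endpoint, and 65.4% is not a measurement on these participants. This part of the reply stands.

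A reader might also infer that treating missing quit attempts as unchanged cannot mean anything. That goes too far. Attempts since starting the sensor are zero at baseline by construction, so no change can be read as no attempt, which is arguably the more natural reading. The plan does not say so, however, and a programmer following the rule would find a recorded baseline answer to carry.

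The fallback also reaches fewer people than general attrition suggests. It applies only without a day-14 or day-28 response. The item is cumulative, so a day-14 yes remains true at day 28. Section 7.5 sends the day-28 questionnaire to everyone, with reminders as needed, and the completer analysis is unaffected. The 15.9% row is therefore an illustration, not a forecast.

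Finally, a matched pre-sensor window is not a clean control. Entry requires current daily smoking of at least 10 cigarettes, whereas an attempt requires a smoke-free day. Selection can therefore depress the rate just before entry, and a before-after rise could appear with no sensor effect. This stands, and it limits the new comparison to a supportive role.

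**Conclusion.** The general rules in Section 10.2 do not fit the quit-attempt endpoint. The windows appear to differ about 13-fold, subject to the inference about the redacted questionnaire. The stated comparators, zero and an external 5%, disagree with each other, and neither is a like-for-like reference from the study's participants. The planned n of 16 is unaffected.

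The coding of participants with no post-baseline response is undefined. Under the assumptions in step 4 and a true rate of 5%, the gap between the two readings is 3.3 points (8.0 − 4.75), 6.5 points (11.0 − 4.5) or 10.4 points (14.6 − 4.2). The size depends on the assumed missing fraction and on the borrowed 65.4%. That the rule needs a stated meaning does not.

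**What to change.** 1. Add one item to the Baseline Questionnaire with the endpoint's wording and a 28-day look-back that ends before first use of the sensor. Compare any attempt in those 28 days with any attempt by day 28 by McNemar, which Section 10.2 already includes for paired two-category data. Report it as a supportive analysis beside the 5% benchmark, and state that selecting current daily smokers can lower the pre-sensor rate and so favour the sensor.
2. In Section 10.2, state that for the day-28 endpoint, participants with neither a day-14 nor a day-28 quit-attempt response count as having made no attempt, and that the general own-control wording does not govern the main analysis of this endpoint.
3. Reconcile the zero comparator in Section 6.3 with the 5% comparator in Section 6.6, so that one is named as the planned test.

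The cost is one questionnaire item and a few sentences. The paired sample sizes worked out above need no increase in enrolment.

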## 9. TECHNICAL APPROACH AND STUDY DESIGN

### 9.1 ACCEPTANCE CRITERIA

Data will be accepted if the participant meets eligibility criteria, and completes the electronic informed consent form, web registration, at least one breath sample (as indicated the Sensor-Only app) and the Baseline Questionnaire.

## 10. STUDY RESULTS

### 10.1 DATA COLLECTION AND CONFIDENTIALITY

Participants will be assigned a unique participant ID which will be used for data collection. Data collection will take place on electronic case report forms (CRFs)

completed by study participants and through data collected in the Sensor-Only app (participant breath sensor usage and CO values of breath samples). CRFs will be reviewed by the study team prior to the end of the study to ensure completeness. Access to electronic CRFs will be limited to necessary study personnel. Study data will be kept in a secure database by the investigator. This database will be accessible only by necessary study personnel. The database will not contain personal identifying information; all subject data in the database will be associated with study identification numbers. The data will be kept for a minimum of 5 years. The data shall be retained for a maximum period of time that is equivalent to the design and expected life of the Pivot Breath Sensor device or the duration of the study sponsor's (Carrot Inc.) existence, whichever is the shortest of the two.

Data on the breath sensor will be accessed with an app customized for this study. This Sensor-only app is our commercially available app with select function disabled. The app to be used in this study will request location permissions in order to complete the Bluetooth scanning and pairing process with the sensor. Other features to access functionality (e.g camera, microphone) are disabled for this study. With regard to the information we will collect, we, the study sponsor, associate each logged in user to a user Id that is a unique identifier which is generated randomly on account creation. We will periodically synchronize logs from the sensor and upload them based on this user\_Id only. The breath samples we collect only contain information regarding: Sample Id, Sample Type, SampleValue, Sample Time. When we upload this information, the only additional information included would be the App build information and user's Sensor ID. We comply with HIPAA and state this in our privacy and terms of use on our website. As such we adhere to HIPAA's Breach Notification Rule should a data breach occur. We take careful measures to prevent a data breach including use of encryptions, secure connections, and limited access to data.

## 10.2 ANALYSIS

Changes in measurements from baseline will be assessed at different timepoints in the study. Participants will serve as their own controls and comparisons will be made to no change. One sample t-test will be used for numerical data. Fisher's Exact or Chi square tests will be used for categorical data. Analyses will be conducted to calculate mean (SD) for normally distributed variables for actual data or mean (SE) for modeled data and median (interquartile range) values in instances of non-normally distributed variables.

McNemar test will be used for 2-category match-paired data. Cohen kappa statistic will be used for 3-category match-paired data. To evaluate changes in attitudes or cigarettes smoked per day over time, repeated measures linear mixed model analyses will be performed using a compound symmetric correlation matrix to model the repeated measures within subjects. To make specific comparisons across time, F statistics will be computed using the results from the model. Statistical significance is set at  $P < .05$ .

Analyses for the outcomes will be evaluated for only those who complete the survey (i.e. completer) and assessed to take into account missing data. To be included in any completer analysis the participant must provide a baseline response and the outcome response. For outcomes that are missing data, these will be assessed pending the data type.

For categorical data, the last response post-baseline will be carried forward for the day 28 analysis and the last response post-28 days will be carried forward for the day 84 assessment. If there is not any data to carry forward, the data will be considered unchanged from baseline. Numerical data will use linear mixed modeling.

All deviations from the study protocol will be identified, recorded and analyzed.

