## **6.6 SAMPLE SIZE AND JUSTIFICATION**

This study will enroll up to 220 participants. Consideration for the sample size included powering the study to observe a clinically meaningful change from baseline for the primary and secondary endpoints using 80% power at a statistical significance of  $P < 0.05$ . The primary endpoint utilized preliminary data from a similar 37 participant pilot study. Data at the 14-day time point showed 31%, 66% and 3% of participants had increased, unchanged and decreased Stage of Change, respectively, from baseline. To detect a statistically significant change in these proportions requires enrolling 50 participants.

The estimated proportion of participants achieving  $\geq 1$  quit attempt is 25% based on interim results from the pilot study. Based on the median prevalence of 65.4% for past-year quit attempts in the general population [13], the average monthly quit attempt rate is approximately 5%. To show that a proportion of 25% of participants making a quit attempt by day 28 is statistically different from 5% will require  $n=16$ .

Finally, literature indicates approximately 1% of the general population [14-18] and 2-5% of individuals in cigarette reduction studies [19, 20] will reduce their CPD by  $\geq 50\%$  on a monthly basis. Assuming that 10% of participants in the present study reduce their CPD by  $\geq 50\%$  by day 28, the present study will require  $n=185$  to show a difference from 5%. Taking these analyses into consideration along with expected attrition, the present study will enroll up to 220 participants.

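### The two powered secondary endpoints and all visit-by-visit comparisons are judged at P<.05 with no gate, adjustment or exploratory label; a fixed order over the three day-28 endpoints would cost almost no power on the plan's own assumptions.

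*Combined protocol and SAP*

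**What the plan says.** Section 6.3 sets one primary endpoint at one visit: "The primary endpoint will assess any change in the proportion of participants' Stage of Change response at day 28 compared to baseline". Under "The secondary endpoints include" it lists two more, both by day 28: at least one quit attempt, and a reduction in cigarettes per day (CPD) of at least 50%.

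Section 6.6 describes "powering the study to observe a clinically meaningful change from baseline for the primary and secondary endpoints", "using 80% power at a statistical significance of" P<0.05. It sizes the three endpoints one at a time: 50 participants for Stage of Change, 16 for quit attempts (25% against 5%) and 185 for CPD reduction (10% against 5%). A secondary endpoint therefore has the largest requirement.

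Section 10.2 is broader. It says "Changes in measurements from baseline will be assessed at different timepoints in the study", with no change as the comparator, and adds for the mixed model: "To make specific comparisons across time, F statistics will be computed using the results from the model". One threshold serves all of this: "Statistical significance is set at" P<.05. The visible text gives no testing order, gate, division of alpha or adjustment, and does not call any comparison exploratory.

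**The concern.** Section 6.6 gives the secondary endpoints the standing of claims, since each has its own power calculation and one of them sets the scale of enrolment. Section 10.2 then gives them no protection. A secondary result below .05 could be reported as significant whether or not the primary endpoint succeeded, and so could a day-7 change in confidence. Some of the many outcome-by-visit results will probably cross .05 by chance, and the plan has no rule for how such a result may be described. The study is open label and uncontrolled, and section 11 discloses that the investigators hold equity in the sponsor. Fixing in advance which results support claims is a cheap safeguard.

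**Working it through.** **1. Reproduce the plan's figures (6.6).** One-sample proportion, normal approximation, two-sided .05 (6.6 does not state sidedness), 80% power:

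n = [(1.960·√(p0·q0) + 0.842·√(p1·q1)) / (p1 − p0)]²

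- CPD reduction, 10% against 5%: 184.8, so 185 (plan: 185).
- Quit attempt, 25% against 5%: 15.7, so 16 (plan: 16).
- Stage of Change, 31% improved and 3% worsened (pilot, day 14): a two-sided McNemar calculation gives 31.6, so 32. The plan's 50 does not reproduce, but it errs on the safe side and does not affect this point.

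**2. The two secondary endpoints.** With both null hypotheses true and independent tests at .05: 1 − 0.95² = 0.0975. At an assumed correlation of 0.5 it is 9.1%, and at 0.9 it is 7.0%. These figures take 5% as the benchmark for both. Section 6.3 compares quit attempts with zero, and a test against zero has no 5% error rate: a single reported attempt refutes it.

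**3. The other comparisons.** The plan gives no number of tests, so the counts below are read from the schedule in 7.7:

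- Widest: six attitude items at 5 follow-ups (30), CPD at 6, two abstinence measures at 5 (10), quit attempts at 4. 30 + 6 + 10 + 4 = 50.
- Without readiness (not listed as an outcome in 6.3), abstinence (no baseline item in 7.7) and quit attempts: 5×5 + 6 = 31.
- Those six outcomes at days 28 and 84 only: 6×2 = 12.

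Each count includes the Stage of Change test at day 28. Leaving it out gives 49, 30 and 11, which changes little.

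Chance of at least one false positive when no outcome changes, 1 − 0.95^k for independent tests, and equicorrelated normal test statistics otherwise (the correlations are assumptions):

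| Tests | Expected false positives | Independent | Correlation 0.5 | Correlation 0.9 |
|---|---|---|---|---|
| 12 | 0.6 | 46% | 32% | 13% |
| 31 | 1.55 | 80% | 51% | 17% |
| 50 | 2.5 | 92% | 62% | 19% |

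**4. Power under a fixed sequence.** Order: Stage of Change, quit attempt, CPD reduction, each at two-sided .05. At n = 185, √n = 13.60.

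- Step 1: discordant share 0.31 + 0.03 = 0.34, difference 0.28. Power = Φ[(0.28·13.60 − 1.960·√0.34)/√(0.34 − 0.28²)] = Φ(5.21), above 99.9%.
- Step 2: Φ[(0.20·13.60 − 1.960·√0.0475)/√0.1875] = Φ(5.30), above 99.9%.
- Step 3: Φ[(0.05·13.60 − 1.960·√0.0475)/√0.09] = Φ(0.843) = 80.0%.

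CPD power is 80.0% tested alone and 80.0% through the sequence. At n = 220 it is 85.3% both ways. Bonferroni over the three endpoints would cut it to 70.1% and 76.8%.

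**5. Sensitivity to the primary effect.** Assumed smaller shifts, steps treated as independent:

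| Improved vs worsened | Step 1 power, n=185 | CPD power through sequence, n=185 | n=220 |
|---|---|---|---|
| 31% vs 3% (plan) | >99.9% | 80.0% | 85.3% |
| 20% vs 5% | 98.7% | 79% | 85% |
| 15% vs 5% | 86.6% | 69% | 78% |
| 12% vs 5% | 63.8% | 51% | 61% |

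**The case against.** The plan already has a hierarchy. Section 6.3 names one primary endpoint at one visit and two secondary endpoints, and 6.6 powers exactly those three, so a reader can tell them from the rest. This stands. A reader might infer that the primary result itself is compromised, or might take the 14.3% for three independent tests (1 − 0.95³) as the study's error rate. The documents do not support either: testing other outcomes does not raise the error rate of a single prespecified primary test.

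A reader might also take 92% as the false-positive risk of the plan. That is not supported. The figure counts every schedule cell as a test, although 10.2 does not say that every visit will be tested. It includes abstinence, which has no baseline, and quit attempts, which 6.3 compares with zero. It also assumes independence between repeated answers from the same people. Nor can the count simply be doubled for the completer and missing-data versions, because 10.2 describes carry-forward of categorical data only for days 28 and 84. What survives is a range, and its lowest value here, about 13%, is still above 5%.

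It can be said that a fixed sequence is not free. This stands in part. The primary effect comes from a 37-participant pilot at day 14. Participants who enter intending to quit within 30 days already hold the top answer, and the quota table sets only a minimum of 20% for that group. A smaller shift is plausible, and step 5 of the working shows its cost.

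Finally, the stated objective is to collect data, and 10.3 accepts a slide report, so formal error control may seem out of proportion. But 6.6 chose to power the secondary endpoints and 10.2 chose to set a significance threshold. Having done both, the plan should say which results may be claimed.

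**Conclusion.** The concern holds in a limited form. The primary test is sound on this point. The two secondary endpoints carry up to a 9.75% chance of at least one false claim when both null hypotheses hold, assuming independence and a 5% benchmark for each. The unlabelled comparisons carry a 46% to 92% chance of at least one chance finding if independent, and about 13% to 19% at an assumed correlation of 0.9, for counts from 12 to 50. Those counts are readings of the schedule, not figures in the plan. A fixed sequence over the three endpoints leaves CPD power at 80.0% (n = 185) or 85.3% (n = 220), but only if the primary effect is near the pilot's. It does not control the remaining comparisons, which is why they need an exploratory label. This is worth correcting before analysis; it does not undermine the primary endpoint.

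**What to change.** First reconcile the quit-attempt comparator: zero in 6.3, 5% in 6.6. Add the 5% CPD benchmark to 6.3, which gives none. In 10.2, name a paired test of improved against worsened for Stage of Change. That section now assigns Cohen's kappa, a measure of agreement, to three-category paired data.

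Then add one paragraph to 10.2. Test at two-sided .05 in this order, and stop making claims at the first non-significant result:

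1. Stage of Change at day 28.
2. At least one quit attempt by day 28, against 5%.
3. CPD reduction of at least 50% by day 28, against 5%.

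Label all other outcomes and visits exploratory, and report them as estimates with 95% confidence intervals and no claim of significance.

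The cost is a short amendment to 6.3 and 10.2. Exploratory results lose the label significant, and the CPD claim becomes conditional on the first two steps, with the loss of power shown above if the primary shift is weaker than in the pilot.
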